#### Methods:

- **a.** Breastfeeding outcomes: Our **exposure** will be randomization group and our **outcomes** will be amount of breastfeeding versus formula feeding, duration of any breastfeeding and duration of exclusive breastfeeding. Study staff will administer validated breastfeeding outcome questionnaires every other week via text message or email to quantify duration of exclusive and any breastfeeding. Statistical analysis: We will use independent samples t-test to analyze the association between participation in the lifestyle intervention program on breastfeeding rates during each timepoint of questionnaire administration. Next, we will use multivariate logistic regression to further examine the adjusted association of lifestyle intervention with rates of breastfeeding, adjusting for key covariates.
- **b.** Breastmilk composition: Our **exposure** will be participation in the lifestyle intervention program. Our **outcomes** will be breast milk cytokines, PUFAs, leptin and insulin. Study staff will instruct mothers to collect breast milk samples and provide a 20 mL sample for this study. Participants will provide breast milk samples before initiating the intervention and then at routine study visits scheduled at 3- and 6-months following intervention initiation. If mothers indicate that they plan to stop breastfeeding based on questionnaires, we will attempt to collect a breast milk sample prior to cessation of breastfeeding. PUFAs will be measured using established methods of ultra-high performance liquid chromatography-heated electrospray ionization tandem mass spectrometry UHPLC-HESI/MS-MS. Insulin will be measured using ELISA or radioimmunoassay. For statistical analysis, we will use independent samples t-test to analyze the association between participation in the lifestyle

intervention program and the mean concentrations of these breast milk markers. We will then use multivariate logistic regression to further examine this association, adjusting for key covariates.

**c.** Procedures: At each study visit, if a participant is still breastfeeding and consent has been signed for this ancillary sub-study, study staff will collect one 10-20mL sample of breast milk. Instructions will be provided at the previous study visit so that if desired, a participant can pump their sample at home in the morning before arrival. If the sample is provided at the study visit, participants will be asked to pump a full breast using their own pump or a disposable manual breast pump that we provide. If pumped at the visit, study staff will thoroughly mix/shake the full sample and pour 10-20ml into the provided sterile container; if at home, the participant will be given instructions on how to prepare the sample. The remainder of the sample will be returned to the subject. This sample will be carried by the BWH LIPP study staff to BWH where they will be stored in freezers in a secured room in a secured building by subject ID number and date of collection to be used for future analysis.

The impact of the proposed supplemental work lies in identifying modifiable factors that may impact breastfeeding outcomes, offspring growth and adiposity. Results from this study could provide further insight into the role of lactational programming in intergenerational obesity.

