# 11.2 Opt-In Ancillary Studies

## 11.2.1 Breast Milk Collection

Aim: To determine the impact of the lifestyle intervention on breastfeeding outcomes and breast milk composition of the index pregnancy.

Hypothesis: Our overall hypothesis is that women randomized to the lifestyle intervention group will have higher rates of breastfeeding and less pro-inflammatory breast milk composition with a lower omega-6/omega-3 fatty acid ratio.

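### The breast-milk composition analysis leaves its exposure undefined and specifies no usable analysis adjusted for the pre-intervention sample

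*Combined protocol and SAP*

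**What the plan says.** Section 11.2.1 describes an opt-in ancillary study of breastfeeding and milk composition after the index pregnancy.

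- **Hypothesis.** It is stated by assigned arm and covers both outcomes: "women randomized to the lifestyle intervention group will have higher rates of breastfeeding and less pro-inflammatory breast milk composition".
- **Methods a (breastfeeding outcomes).** The exposure "will be randomization group and our" outcomes are amount and duration of breastfeeding. The sentence describing the test nevertheless refers to the "association between participation in the lifestyle intervention program on breastfeeding rates during each timepoint of questionnaire administration".
- **Methods b (milk composition).** The exposure "will be participation in the lifestyle intervention program".
- **Sampling.** "Participants will provide breast milk samples before initiating the intervention and then at routine study visits scheduled at 3- and 6-months following intervention initiation". If a woman indicates that she plans to stop, "we will attempt to collect a breast milk sample prior to cessation of breastfeeding".
- **Analysis in Methods b.** "For statistical analysis, we will use independent samples t-test to analyze the association between participation in the lifestyle" programme and, as the sentence goes on, "intervention program and the mean concentrations of these breast milk markers". A multivariate logistic regression with unlisted key covariates follows.
- **Methods c.** Milk is taken at a visit only from women who are still breastfeeding and have signed the sub-study consent.

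Two places in the parent protocol bear on this. Section 8.2 analyses Aims 1a, 1b and 2 by intention to treat. Section 8.5 stratifies randomisation by overweight versus obese and by breastfeeding status.

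**The concern.** Two things need settling before these samples are analysed.

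The first is who is compared with whom. If participation is taken to mean attendance, women assigned to the intervention who did not attend could be dropped or counted with the controls. The comparison would then partly reflect who adheres. The opening for this is real: Section 4.3 lists missed training sessions among the reasons women have been asked to withdraw, and only the intervention arm has scheduled training sessions.

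The second is what the comparison uses. Each woman's own pre-intervention milk is collected, but no workable analysis uses it. The t-test takes means only and names no time point. The second step is a model for binary outcomes, whereas cytokines, fatty acids, leptin and insulin are measured as concentrations, and no cut-point is given.

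Two related gaps affect interpretation. No rule says whether a pre-cessation sample enters the means. Follow-up milk also exists only for women still breastfeeding, which the sub-study itself expects to differ by arm.

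**Working it through.** The sub-study states no sample size, effect size, standard deviation, alpha or power, so there is no figure of its own to reproduce. The check has three steps.

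**1. Exposure, side by side**

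| Place in 11.2.1 | Exposure named |
|---|---|
| Hypothesis | Randomised arm |
| Methods a, exposure | Randomised group |
| Methods a, test | Participation |
| Methods b, exposure | Participation |
| Methods b, test | Participation |

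No attendance or adherence threshold is given anywhere. The provable defect is an undefined term that disagrees with the hypothesis and with the exposure in Methods a.

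**2. What an as-treated reading could do (all inputs assumed)**

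Take a true effect of zero and equal arms. A share q of the intervention arm is classed as non-participating, with a mean s standard deviations above the control mean. The whole intervention arm keeps the control mean.

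- Non-participants dropped: difference = −qs/(1−q).
- Non-participants moved to control: difference = −qs/(1−q) − qs/(1+q).

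For q = 0.2 and s = 0.5, the first is −0.10/0.80 = −0.125 SD. The second is −0.125 − 0.10/1.20 = −0.208 SD.

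| q (s = 0.5) | Dropped | Moved to control |
|---|---|---|
| 0.1 | −0.06 SD | −0.10 SD |
| 0.2 | −0.13 SD | −0.21 SD |
| 0.4 | −0.33 SD | −0.48 SD |

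Neither q nor s is in the documents. The 40 to 50% dropout in Section 8.3 concerns the parent trial and does not measure q. Analysis by randomised arm removes this source of bias.

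**3. Precision from the pre-intervention sample (correlation r assumed)**

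Relative to a t-test on follow-up values alone, and ignoring a negligible loss of degrees of freedom, ANCOVA multiplies the variance of the arm difference by 1−r². The equivalent sample size multiplier is 1/(1−r²). A simple change score multiplies the variance by 2(1−r).

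| r | ANCOVA variance | Reduction | Equivalent extra women | Change-score variance |
|---|---|---|---|---|
| 0.2 | 0.96 | 4% | 4% | 1.60 |
| 0.3 | 0.91 | 9% | 10% | 1.40 |
| 0.5 | 0.75 | 25% | 33% | 1.00 |
| 0.7 | 0.51 | 49% | 96% | 0.60 |

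The gain is small at low correlation and large only at the upper end. A change score would lose precision below r = 0.5, so ANCOVA is the safer use of the baseline. The correlation may differ between markers and between the 3- and 6-month samples, so no single row applies to all outcomes.

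**The case against.** A reader might infer that the sub-study abandons randomisation. The documents do not support that. Methods a names the randomised group as exposure and then describes its own test in terms of participation, so the authors seem to use the word loosely for assigned arm. The hypothesis is by randomised arm, no as-treated group is defined, and the parent aims are analysed by intention to treat. This part of the objection stands: the text permits an as-treated analysis but does not prescribe one.

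A reader might also infer that the baseline sample is certain to go unused. That is certain only for the t-test. The unlisted covariates of the second step could include the pre-intervention concentration. This stands too, but it does not rescue the plan, because that step is a logistic model and no binary outcome is defined for it.

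Ignoring the baseline costs efficiency and does not bias a comparison by randomised arm. That is correct, and at r of 0.2 to 0.3 the cost is 4 to 9% of the variance.

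Finally, the proposed change does not cure selection on continued breastfeeding. Defining the comparison by arm creates no milk after a woman has stopped. Pre-cessation samples are the plan's only means of capturing women who stop, so keeping them out of the main analysis could increase that selection. Including them mixes unscheduled lactation stages. Both considerations are fair, and the choice is a matter of judgement.

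**Conclusion.** The point holds as a minor one. In Methods b the exposure is undefined and inconsistent with the hypothesis and with the exposure in Methods a. The t-test leaves out the pre-intervention sample, and the second-step model does not fit the type of outcome. As a result, no usable baseline-adjusted analysis is specified. These conclusions rest on the text alone.

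The sizes rest on assumptions. The variance reduction runs from 4% at r = 0.2 to 49% at r = 0.7, with r not given in the documents. The as-treated differences illustrate what the wording would allow and do not predict what will happen.

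Even after correction, the composition result remains conditional on continued breastfeeding, an outcome arising after randomisation, and should be read that way. The sub-study is opt-in and ancillary, and the parent trial's primary analysis of neonatal fat mass is unaffected.

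**What to change.** Amend Section 11.2.1, Methods b, as follows.

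1. State that the exposure is the randomised arm, and use the same term in the test sentences of Methods a and b.
2. Replace the t-test and the logistic regression with a linear ANCOVA or mixed model of concentration at 3 and 6 months after the start of the intervention, on the log scale where skewed. Adjust for the pre-intervention concentration on the same scale and for the randomisation strata (overweight versus obese, breastfeeding status). List any further covariates.
3. State a rule for pre-cessation samples before analysis: in the main model or in a sensitivity analysis, with the reason.
4. Report by arm how many women still gave milk at each time point, and acknowledge that analysis by arm does not remove selection on continued breastfeeding.

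The cost is a change of wording in the addendum. The samples are already planned, and Methods c stores them by subject number and date, so no new data are needed. Women without a pre-intervention sample cannot enter a plain ANCOVA, and the mixed-model form would be needed to keep them.

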covariate-adjusted difference of 146 g fat mass between groups. We have 80% power to detect an absolute or covariate-adjusted difference as small as 126 g fat mass between groups. Corresponding 95% CI for the absolute or covariate-adjusted difference in neonatal fat mass between groups will be reported. For secondary analyses, we will be using the same

statistical approach. Based on our preliminary data, we estimate the SD of birth weight to be 700 g; with 50 neonates in each group we will have 90% power to detect an absolute or covariate-adjusted difference of 455 g in birth weight and 80% power to detect a 393g difference between groups. Additional secondary analyses will include umbilical cord cytokines. Comparisons will be performed using a two-sample t-test at a significance level of  $\alpha$ =0.05; however, Mann-Whitney U tests or log transformations will be employed if data are not normally distributed. Linear regression models, including confounding factors, will be used to perform covariate adjustments. Based on our published data (80), we estimate the standard deviations of umbilical cord IL-6 and CRP to be 3.4 pg/ml and 7,900 ng/ml, respectively. With 50 women in each group, we will have 90% power to detect an improvement in IL-6 and CRP levels of 50% and 42%, and 80% power to detect an improvement of 42% and 36%, respectively.

The primary goal of Aim 2 is to determine the effect of lifestyle intervention prior to pregnancy on placental mitochondrial fatty acid oxidation at term. We hypothesize that placental  $\beta$ -oxidation will be higher in the LIPP group. We will conduct an intent-to-treat analysis using two sample t-test or non-parametric Wilcoxon rank-sum test to assess differences between groups. Regression analysis will be used to assess the association of placental  $\beta$ -oxidation and enzyme activity with maternal inflammatory cytokine levels and insulin resistance in early pregnancy, along with neonatal fat mass with adjustment for gestational age and gender. Descriptive statistics, such as mean, median and range will be calculated for all variables. Power and sample size analysis based on our preliminary mitochondrial  $\beta$ -oxidation data in obese women (38±14 nmol/mg/hr) showed that a sample size of N=18/group achieves 80% power to detect a difference of 25% between groups using a two-sample t-test with a significance level of 0.05.

• *Provide a power analysis.* These are included in the statistical analyses.

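### Breast-milk sub-study: the only adjusted analysis of continuous marker concentrations is logistic regression, and no cut-point is given

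*Combined protocol and SAP*

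**What the plan says.** Section 11.2.1, Methods, part b makes participation in the lifestyle programme the exposure. The outcomes "will be breast milk cytokines, PUFAs, leptin and insulin". The first analysis is an independent-samples t-test relating the "intervention program and the mean concentrations of these breast milk markers", so the markers are treated as continuous. The next sentence gives the adjusted analysis: "We will then use multivariate logistic regression to further examine this association, adjusting for key covariates". Section 11.2.1 gives no threshold, median split or detection-limit rule for any marker, and no sample size, SD or power.

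Part a of the same Methods, on breastfeeding outcomes, has a near-identical sentence in which logistic regression is used to "further examine the adjusted association of lifestyle intervention with rates of breastfeeding".

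Section 8.2 handles the same kind of marker differently in the main trial. It says "Additional secondary analyses will include umbilical cord cytokines" and starts from a t-test. It then provides that "Mann-Whitney U tests or log transformations will be employed if data are not normally distributed" and that "Linear regression models, including confounding factors, will be used to perform covariate adjustments".

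**The concern.** The adjusted model in part b does not fit the outcomes that part b names. With the markers as outcomes, someone must later choose a cut-point for each of several markers before the model can be fitted. Three things follow:

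- The odds ratio answers a different question from the t-test, so the adjusted result cannot be read as the t-test's mean difference after adjustment.
- The size of the odds ratio depends on the cut-point, which is open to choice after the data are seen.
- Splitting a continuous measurement discards information, and the adjusted comparison loses power.

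Part a has a lesser gap. It lists the durations of any and of exclusive breastfeeding as outcomes, but its stated analyses cover only breastfeeding rates at each questionnaire.

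**Working it through.** Section 11.2.1 states no figure, so there is none to reproduce. The main check is of the text; the arithmetic only illustrates the cost.

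**Text, side by side**

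| | Outcome | Unadjusted | Adjusted |
|---|---|---|---|
| 11.2.1 part a | Breastfeeding rates | t-test | Logistic regression |
| 11.2.1 part b | Milk marker concentrations | t-test on means | Logistic regression |
| 8.2, cord cytokines | Concentrations | t-test (rank test or log scale if not normal) | Linear regression |

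Logistic regression fits part a once feeding status is coded yes/no at each questionnaire. It does not fit part b. That the sentence was carried over from part a is an inference; the documents do not say so.

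One reading would need no cut-point: arm as the dependent variable and the markers as predictors. Part b rules this out by naming participation as the exposure and the markers as the outcomes.

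**Power after a split.** Assumptions, none from the documents: normal marker, equal SDs, two-sided 5% test, 80% power on the continuous scale, covariate unrelated to the marker.

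- Noncentrality for 80% power: 1.960 + 0.842 = 2.802.
- Information kept by a split at centile p: φ(c)² / [p(1 − p)], where c is the normal quantile at p.
  - p = 0.50: 0.637.
  - p = 0.75: 0.539.
- Power after the split: Φ(2.802 × √efficiency − 1.960).
  - Median: Φ(0.276) = 0.61.
  - Upper quartile: Φ(0.096) = 0.54.

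These are large-sample values. Comparing two proportions at 15, 25 and 50 per arm gives 58%, 59% and 60% for a median split, and 47%, 50% and 52% for an upper-quartile split. In simulation, adjusted logistic regression after a median split had power 0.57, 0.62 and 0.62 at 25, 50 and 200 per arm, against 0.79 to 0.80 for adjusted linear regression.

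**Odds ratio by cut-point.** Assumed true difference: intervention mean 0.5 SD lower. The cut is placed at a centile of the control distribution.

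| Cut | Control above | Intervention above | Odds ratio |
|---|---|---|---|
| Median | 0.500 | 0.309 | 0.446 |
| 75th centile | 0.250 | 0.120 | 0.409 |
| 90th centile | 0.100 | 0.037 | 0.350 |

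For example, at the median: (0.309/0.691) / (0.500/0.500) = 0.45.

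**With a useful covariate.** If pre-intervention and follow-up concentrations correlate at 0.6 (assumed), linear adjustment multiplies the residual SD by √(1 − 0.36) = 0.8. The noncentrality becomes 2.802/0.8 = 3.50 and power Φ(1.54) = 0.94. Simulated power for logistic regression after a median split, with the same covariate, was about 67% to 72%.

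**The case against.** The strongest reply is that nothing in the plan calls for dichotomising. If the sentence was simply carried over from part a, the analysts will probably fit a linear model and the harm never arises. The sub-study is opt-in and reads as an outline, and its t-test on means remains. This limits how serious the point is, but it does not rescue the text: the adjusted analysis cannot be run as written without a decision that the plan does not make. Section 8.2 does not fill the gap, because it does not mention breast milk and section 11.2.1 sets its own, different method.

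A second reply is that the power figures rest on assumptions and on large samples. That is fair. In very small groups the closed-form value for an upper-quartile split is too favourable: 47% at 15 per arm in the two-proportion calculation, against 54%. They also leave out baseline adjustment, which widens the gap in the worked example. The figures show direction and rough size only.

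Third, a binary definition fixed in advance for each marker would also make the model runnable. It would, but it would keep the loss of information and the mismatch with the t-test.

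Finally, the duration point in part a is a separate matter of missing detail. Rates at successive questionnaires partly describe duration. That stands, and the duration point carries little weight here.

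**Conclusion.** The concern holds. Part b names a model that does not fit its declared outcomes, with no cut-point to make it fit. The consequence is minor: it is confined to the follow-up adjusted model in an opt-in sub-study. Part b's t-test is sound and keeps its power; the main trial and its primary outcome are untouched.

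The conclusion on the text needs no assumption. The illustrated size does: for a normal marker with 80% power on the continuous scale, power falls to about 61% (median split) or 54% (upper-quartile split), and the odds ratio for one assumed 0.5 SD difference runs from 0.45 to 0.35 with the cut.

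**What to change.** Replace the logistic model in part b with linear regression of marker concentration, on the log scale if skewed as section 8.2 allows, at the 3- and 6-month visits after initiation. Specifically:

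- Use randomised arm as the exposure. Part b speaks of participation, but the sub-study's hypothesis and part a are framed by randomised group, so the wording should be aligned.
- Adjust for the pre-intervention concentration, since "Participants will provide breast milk samples before initiating the intervention", and for the weight-class stratum from section 8.5. Include the breastfeeding-status stratum only if it still varies among women giving milk. Name these in place of the unspecified key covariates.
- State that the result applies to women still breastfeeding at the visit, because only they provide milk. The new model states this restriction but does not remove it.
- Say whether the two visits are modelled separately or jointly, and how the samples taken shortly before breastfeeding stops are used.

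Keep the t-test in part b and the logistic model for rates in part a. As a secondary addition, name a time-to-event analysis by randomised arm for part a's two duration outcomes that handles women still breastfeeding at last contact. Kaplan-Meier with Cox regression, or a discrete-time or interval-censored version given the two-weekly questionnaires, would all serve; the choice is the sponsor's.

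The cost is a few lines of text in part b and one sentence in part a. The samples and questionnaires are already planned. The change should be made before the markers are analysed.
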